## 5. STUDY CONDUCT

### 5.1 Subject recruitment, enrollment and randomization

Potential participants will be identified by the clinical personnel of participating institutions. If the potential study candidate is interested in receiving more information and possibly consenting to the study, the research coordinator will reach out to the patient and provide further information about the study, including its procedures and risk and potential benefits. Patients will be given enough time to ask questions, and consider study participation. If the patient continues to express interest, Visit 1 will be scheduled to obtain a written informed consent before any study-specific procedures are performed.

The consent procedure will take place at the initial part of Visit 1. The research coordinator will review the consent form with the patient, discuss risks and benefits of the study and answer questions. The coordinator will ask brief questions about the study procedures to assure the patient's understanding. After the patient signs the consent form, a copy will be provided to the patient (if a copy can't be obtained, two originals will be signed, one retained by the patient and one by CRC).

Patients who sign the consent form will be considered enrolled in the study. Enrolled patients will be assigned a unique enrollment number. The unique enrollment number is a 4 digit number made up of the site number followed by the patient number. If a patient is discontinued from the study their enrollment number will not be re-used and the patient will not be allowed to re-enter the study.

The consenting patient will participate in the Screening/OIC Confirmation/Baseline period, during which eligibility for randomization will be determined. Patients who are eligible will be enrolled into EDC. If a patient discontinues from participation in the study, then his/her enrollment/randomization code cannot be reused.

### **5.1.1 Procedures for randomization**

Eligible patients will be randomized in blocks to receive either 25 mg naloxegol or placebo in a 1:1 ratio. Bottle numbers will be assigned sequentially as patients become eligible for randomization. The clinical research coordinator will contact the randomization coordinator at [REDACTED] to obtain the bottle number for the subject. Patients who discontinue early from study will not be replaced. If a bottle is allocated incorrectly there will be no attempt to be remedy the error once the study drug has been dispensed.

## **5.2 Procedures for handling subjects incorrectly enrolled, or randomized, or initiated on investigational product**

Patients who fail to meet I/E criteria should not under any circumstances be enrolled or received study drug. If a patient who does not meet selection criteria is randomized in error or is incorrectly started on treatment, a discussion should occur between the medical monitor and the investigator regarding whether to continue or discontinue the patient from treatment.

## **5.3 Blinding and procedures for unblinding the study**

### **5.3.1 Methods for ensuring blinding**

Naloxegol 25 mg and placebo will be identical in size and color. Packaging and labeling of study drug will be in a way to ensure blinding. Patients will receive 1 tablet once per day.

### **5.3.2 Methods for unblinding the study**

The treatment number should not be broken except in medical emergencies when the appropriate management of the patient requires knowledge of the treatment randomization. The study site will contact the medical monitor to discuss unblinding. If it is necessary to unblind the subject, the randomization coordinator at [REDACTED] will provide the unblinded drug assignment. The study site will provide documentation of unblinding to [REDACTED]

## 5.4 Treatments

### 5.4.1 Identity of investigational product(s)

Table 2

| Investigational product       | Dosage form and strength | Manufacturer |
|-------------------------------|--------------------------|--------------|
| Naloxegol                     | Tablet 25 mg             | [REDACTED]   |
| Matching Placebo to Naloxegol | Tablet 0 mg              | [REDACTED]   |

### 5.4.2 Doses and treatment regimens

Patients will receive study drug during:

- The 14 day randomized period of the study
- The 14 day open-label period of the study

Patients will be instructed to take 1 tablet, 1 hour before eating in the morning. Naloxegol or placebo will be taken once daily as 1 tablet. Tablets will consist of naloxegol 25 mg or placebo.

### 5.4.3 Additional study drug

Sites will obtain bisacodyl for use as rescue medication and will dispense bisacodyl to patients at Visits 2 and 3.

### 5.4.4 Labeling

The clinical trial material will be clearly marked according to national requirements regarding use for clinical trial investigation only and will also be labeled with the drug name, study reference number, and storage conditions. It is the responsibility of the investigator to ensure that accurate accountability records are maintained throughout the study.

[REDACTED] will provide the unblinded study drug (naloxegol 25 mg tablets and identical-appearing placebo tablets) in bulk unlabeled bottles to [REDACTED] who will be responsible for bottling, blinding, and labeling the study medication. Labels will be prepared in accordance with Good Manufacturing Practice (GMP) and local regulatory guidelines.

### 5.4.5 Handling and Storage

The randomization coordinator at [REDACTED] will maintain the unblinded kit log and sequential randomization log for all study sites. When patients become eligible for randomization the study site will contact the randomization coordinator at [REDACTED] to obtain the next sequential bottle number. The study sites will be blinded to the randomized assignments and will only be given the bottle number.

All study drug must be kept in a secure place under appropriate storage conditions. A description of the appropriate storage and shipment conditions is specified on the study drug label and in the Investigators' Brochure. All study drug will be stored in original containers and dispensed to the

study patients. The receipt, handling, storage, and dispensing of naloxegol will be in accordance with applicable country regulatory requirements.

## 5.5 Concomitant and post-study treatment(s)

It is recognized that some patients may have their pain managed by personal physicians who are not connected with the study. In these cases, the investigator should notify the patient's personal physicians of the patient's participation in the study, and to ask the physician to notify the study investigator should a change in their pain control regimen be made.

Concomitant non-opioid analgesics will not be prohibited, but investigators will be encouraged to maintain such drugs at stable doses on-study if possible.

Contraceptives (eg, oral contraceptive, implant, dermal contraception, long-term injectable contraceptive, intrauterine device) are allowed.

Patients who were on a maintenance bowel regimen (i.e. regular daily schedule) are allowed to continue on that regimen for the duration of the study. Patients who use laxatives on as needed basis (or those who do not use laxatives) will be required to stop all laxatives and other bowel regimens at randomization for the duration of the study. Bisacodyl will be provided at visit 2 for use during the study. During all treatment periods of the study if after a minimum of 48 hours the patient has not experienced a bowel movement they may take bisacodyl rescue therapy (10 to 15 mg dose). However, in the case the patient is unable to wait 48 hours to receive rescue laxative, rescue laxatives may be administered sooner than 48 hours at the discretion of the investigator. If the patient remains constipated, bisacodyl rescue therapy may be repeated up to 2 additional times, as necessary, each 10 to 15 mg doses administered at 12-hour intervals, or the investigator may prescribe a one-time use of an enema. The timing and administration of any rescue therapy used will be noted and recorded in the diary.

Patients will be instructed on the guidelines for rescue bisacodyl use. Patients will be asked to return unused bisacodyl at each subsequent visit. Documentation of bisacodyl use will be reviewed with the patient at each visit by comparing returned bisacodyl with diary records. If there is a discrepancy, the patient will be counseled regarding proper documentation of bisacodyl use in the diary.

Patients will be asked to record their daily opioid breakthrough medication use in the paper diary. Changes in the opioid regimen and laxative regimen may occur at the discretion of the investigator to ensure appropriate symptom management throughout the study.

The following laxative medications are prohibited during the study period:

- Lubiprostone (Amitiza®)
- Linaclotide (Linzess)
- Drugs blocking fat absorption with an associated laxative effect
- Prucalopride
- Any agent that is used in an off-label fashion to treat constipation (eg, colchicine, misoprostol, erythromycin, cholinesterase inhibitors such as donezepil)

- Any experimental constipation therapy.

The following opioid antagonists and mixed agonists/antagonists are also prohibited:

- Pentazocine
- Buprenorphine
- Nalbuphine
- Naloxone and other naloxone containing products, such as oxycodone/naloxone combinations (eg, Targin)
- Naltrexone and other naltrexone containing products such as morphine/naltrexone combinations (eg, Embeda)
- Methylnaltrexone (Relistor®)
- Alvimopan (Entereg®).

The following strong inhibitors of CYP3A4 enzymes and p-glycoprotein (PGP) are prohibited; examples are provided below:

- Cyclosporine
- Indinavir
- Nelfinavir
- Ritonavir
- Ketoconazole (except for topical use)
- Itraconazole
- Verapamil

Chemotherapy:

- Concurrent chemotherapy is allowed during the study for patients who have received and recovered from at least 1 cycle of the current chemotherapy regimen prior to study entry
- Patients will not be permitted to begin a new chemotherapy regimen during the study period
- Other medication, which is considered necessary for the patient's safety and well-being, may be given at the discretion of the investigator and recorded in the appropriate sections of the eCRF.

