### **4.1 Inclusion criteria**

To be eligible for the study, patients must meet the following criteria:

- Men and women aged 18 or older: Women of child bearing potential must have a negative urine pregnancy test during the Screening/OIC Confirmation/Baseline period, a history of no sexual activity or consistent use of an effective birth control method for at least 12 weeks prior to the study, and agreement that no sexual activity or the method of birth control will be continued during the study and for a period of 8 weeks after it ends; male patients who are sexually active must agree to use a barrier method of contraception (condom with spermicide) from the first dose of IP until 12 weeks after their last dose
- Able to follow instructions in English, give informed consent and to answer patient reported outcomes (PRO) questions by himself/herself; the patient will provide written informed consent before initiation of any study-related procedures
- Active cancer of any type with an investigator-estimated life expectancy  $\geq$  8 weeks and a Palliative Performance Status scale score  $\geq$  30%
- Patients receiving concurrent chemotherapy must have received and recovered from a minimum of 1 cycle of the current chemotherapy regimen upon consenting to the study and be considered stable in the opinion of the investigator
- Chronic cancer-related pain, defined as pain for a minimum of  $\geq$ 2 weeks which on review by the investigator, can be attributed to the neoplasm or its treatment
- Daily treatment with an opioid drug which is taken at a dose equal to or greater than 20 mg morphine or its equivalent for at least one week, with no expectation of a decrease greater than 25% or an increase greater than 100% during the study period.
- Patients may or may not be on a stable laxative regimen, defined as daily use at a stable dose for  $\geq$ 7 days; if the patient is taking a stable dose, he or she must be willing to remain on that regimen for the 7 day confirmation period without titration or adjustments.

History of constipation, defined through history and through participation in the Screening/OIC Confirmation/Baseline period:

- Patient history must include 2 or more of the following during defecations occurring in the two weeks prior to screening:
  - <3 spontaneous bowel movements per week
  - hard/lumpy stools (Bristol Stool Scale Type 1 or 2) in more than 25% of defecations
  - sensation of incomplete evacuation in more than 25% of defecations

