  - sensation of anorectal obstruction in more than 25% of defecations
  - Straining during more than 25% of defecations

**Note:** (spontaneous bowel movements (SBMs) are defined as not using a laxative if not already taking daily laxatives, or if taking daily laxatives, not using an additional laxative).

- Confirmation during the 7-day OIC confirmation period must include at least 2 or more of the following symptoms:
  - <3 SBMs per week
  - hard/lumpy stools (Bristol Stool Scale Type 1 or 2) in more than 25% of defecations
  - sensation of incomplete evacuation in more than 25% of defecations
  - sensation of anorectal obstruction in more than 25% of defecations
  - Straining during more than 25% of defecations

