##### **10.2.1.1 SBMs Responder Rate**

A SBM is defined as a BM without rescue laxatives in the previous 24 hours. Days with no BMs should be recorded as zero, rather than missing. This diary data will be used to identify SBMs. The weekly SBM frequency within each time period will be calculated for each patient as:

(Total number of SBMs during the time period of interest/number of days) x 7,

where the denominator is the number of days during the time period in which the patient records data. If less than 4 days of data are recorded within a particular week, the data for that week will be considered insufficient and the rate will be set to missing for that week.

A responder is a patient with  $\geq 3$  SBM in a week and at least one SBM/week increase over baseline for the two weeks during which the study drug is taken. For the purposes of the analysis, the proportion of responders will be evaluated during the randomized period, and also during the extension period. The randomized period permits a comparison of response rates for those who received naloxegol and those who received placebo. The responder rate during the extension period for those patients who entered the extension period after having had placebo will be evaluated as supportive of the response rate determined during the randomized period.

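### A scheduled laxative increased or added after randomization does not disqualify a bowel movement, so it can turn a non-responder into a responder and, if naloxegol works, can dilute the secondary responder comparison

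*Combined protocol and SAP*

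**What the plan says.** Four parts of the combined protocol and SAP bear on this.

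- **Laxatives before randomization (4.1).** For a patient on a stable daily laxative, "he or she must be willing to remain on that regimen for the 7 day confirmation period without titration or adjustments". Nothing equivalent is stated for the 14-day blinded period.
- **Laxatives after randomization (5.5).** Patients on a regular daily bowel regimen "are allowed to continue on that regimen for the duration of the study". As-needed users and non-users "will be required to stop all laxatives and other bowel regimens at randomization for the duration of the study". Later the same section says: "Changes in the opioid regimen and laxative regimen may occur at the discretion of the investigator". The stated purpose is symptom management, and no period of the study is excepted.
- **Scoring (10.2.1.1).** "A SBM is defined as a BM without rescue laxatives in the previous 24 hours". SBMs are identified from the diary. A responder needs at least 3 SBMs in a week and "at least one SBM/week increase over baseline for the two weeks during which the study drug is taken". No condition refers to a change in scheduled laxative.
- **Eligibility note (4.1).** Here an SBM is defined differently. For a patient on a daily regimen the condition is "if taking daily laxatives, not using an additional laxative". This wording is not carried into 10.2.1.1.

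Section 11.2.2 compares responder proportions between arms on the ITT denominator. It has no rule or sensitivity analysis for laxative changes. The only laxative item listed for the diary (6.2.3) is bisacodyl rescue. Other rescue laxatives go on the concomitant medication eCRF page (6.2.9), and Visit 3 reviews scheduled and as-needed medications and doses (3.2.3).

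**The concern.** Baseline is recorded on a fixed laxative regimen, but the treatment weeks need not be. A daily user who does poorly after randomization can have the scheduled dose raised. The extra BMs then count towards both the threshold of 3 per week and the gain of 1 per week over a baseline measured without the increase. The stated reason for allowing changes is symptom management, so poor response is a natural trigger.

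At stake is the between-arm difference in responder rate. Section 11.1 says this pilot is meant to show whether there is an efficacy signal and how large the effect is, as input to a bigger trial. A diluted difference would make that input too small. The primary endpoint, the difference in adverse events (10.1), is not affected.

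**Working it through.** **The plan's own figure.** Section 11.1 gives 22 per group for a difference of 0.58, 70% power and two-sided 10% error, based on SBMs per week.

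- Read as a standardized difference: n = 2 × (1.645 + 0.524)² / 0.58² = 28 per group, and 22 per group gives about 61% power. On this reading the figure does not reproduce.
- Read as raw SBMs per week: the SD would have to be 0.58 / (2.169 × √(2/22)) = 0.58 / 0.654 = 0.89. No SD is stated, so the figure cannot be settled.
- It concerns SBM frequency, not the responder rate, and nothing below depends on it. Only 22 per arm and two-sided 10% are carried forward.

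**Model.** The documents give no responder, escalation or conversion rates, so all of these are assumptions.

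- True responder rates: 60% naloxegol, 40% placebo.
- e = share of non-responders whose scheduled laxative is escalated, 0.2 to 0.4 in each arm.
- c = share of those who then meet the responder rule, 0.4 to 0.6. Let k = e × c.
- Observed rate = p + (1 − p)k. With equal k in both arms, observed difference = true difference × (1 − k).
- Extra responders per arm = 22 × (1 − p) × k.
- Power: two-proportion z-test with pooled standard error se0 under the null and unpooled se1 under the alternative, both rejection tails counted. This stands in for the test named in 11.2.2.

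| e | c | k | Placebo | Naloxegol | Difference (points) | Extra responders, placebo v naloxegol | Power |
|---|---|---|---|---|---|---|---|
| 0 | – | 0 | 40.0% | 60.0% | 20.0 | 0 v 0 | 37% |
| 0.2 | 0.4 | 0.08 | 44.8% | 63.2% | 18.4 | 1.1 v 0.7 | 34% |
| 0.2 | 0.6 | 0.12 | 47.2% | 64.8% | 17.6 | 1.6 v 1.1 | 32% |
| 0.4 | 0.6 | 0.24 | 54.4% | 69.6% | 15.2 | 3.2 v 2.1 | 27% |

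The 18.4-point row worked through: pooled rate 0.540, se0 = √(2 × 0.540 × 0.460 / 22) = 0.150, se1 = √((0.448 × 0.552 + 0.632 × 0.368) / 22) = 0.148. Then Φ((0.184 − 1.645 × 0.1503) / 0.1477) = 0.334, and the other tail adds 0.002, giving 0.336.

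**Sensitivity to the assumptions.**

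- Rarer escalation, e = 0.05 and c = 0.5: k = 0.025, difference 19.5 points, power 36%.
- Other true rates with more conversion, 50% v 30% and k = 0.3: 65% v 51%, so 20 points become 14 and power falls from 38% to 24%.
- No drug effect, equal k: the difference is 0 × (1 − k) = 0. The expected difference is unchanged and the mechanism does not inflate type I error.

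**Timing.** The model ignores when the change happens. If 10.2.1.1 requires both weeks to qualify, a patient who has already failed week 1 cannot be converted in week 2. Only early changes could then matter, and the losses above are upper values for the assumed e and c.

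**The case against.** The case against has several parts.

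- **Frequency is unknown.** The blinded period lasts 14 days, with one required call at about 72 hours and no visit until Visit 3. Non-response already has a route in 5.5, bisacodyl rescue, and that does disqualify BMs. Escalation of scheduled laxatives may be uncommon. This stands. Even at the top of the assumed range the imbalance is about 1 patient (3.2 v 2.1 per 22).
- **Added laxatives may be covered.** The note in 4.1 excludes BMs after an additional laxative, and 6.2.9 recognizes rescue laxatives other than bisacodyl, so a laxative added for non-response might be classed as rescue. This stands in part. The note is not in the analysis definition, and it does not clearly reach a higher dose of the laxative already taken. That dose increase is the clearest gap.
- **Starting a laxative is contested.** For as-needed users and non-users the stop instruction in 5.5 conflicts with the later discretion sentence. A reader might infer that investigators may freely start scheduled laxatives in anyone. The documents do not support that; the two statements need reconciling.
- **ITT permits it.** Counting outcomes whatever background care was given is a legitimate question. But an endpoint built on spontaneous BMs already treats laxative-driven BMs as not being response, so silence on scheduled changes is a gap in the scoring rule.

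**Conclusion.** The point holds as a possibility that the plan leaves open. Under the wording of 10.2.1.1, BMs from a scheduled laxative increased or added after randomization can count as SBMs, against a baseline recorded without it. If naloxegol works, this can convert more placebo than naloxegol patients and shrink the difference. Under the stated assumptions 20 points become 18.4 to 15.2 and power falls from 37% to 34-27%, and by less if escalation is rarer or both weeks must qualify.

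Two stronger readings are tempting. A reader might infer that the placebo responder rate will be raised. The documents give no escalation rate, and the placebo excess in the model requires an active drug. A reader might also infer a risk of a false positive result. With no drug effect and intact blinding the expected difference stays zero. The endpoint is secondary in a pilot, so this is an inexpensive improvement to the scoring and does not threaten the primary aim.

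**What to change.** Leave care as it is and change the scoring text.

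1. In 10.2.1.1, align the SBM definition with the note in 4.1, so that an additional laxative also disqualifies a BM. State explicitly how a dose increase of an existing daily laxative is treated.
2. Reconcile the stop instruction and the discretion sentence in 5.5. Which of them should govern is not a matter for this review.
3. For the randomized comparison, score a patient as a non-responder for any week on or after a laxative is started, or its dose increased, following randomization. Rescue doses stay under the existing 24-hour exclusion and do not trigger this rule. State whether both weeks must qualify.
4. Record the start or change date on the concomitant medication eCRF page.
5. Report escalations by arm, and give the as-written scoring as a sensitivity analysis.

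The rule works by week. A 24-hour rule for each BM would need dose times for scheduled laxatives, which neither the diary nor the Visit 3 review is stated to collect.

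The cost is a few sentences, one date field and one extra table. The downside is that a few patients whose laxative was changed for other reasons will be scored as non-responders; the sensitivity analysis shows how much that matters.
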